12.5 Completion Interview

After the completion of dosing, (as soon as possible after the last dose of investigational product is taken during Study Week 12) or at the time of premature study discharge, subjects will be asked to complete the study completion interview. Vital signs, physical examination, a 12-lead ECG, pregnancy test and clinical laboratory studies (blood chemistry, hematology, and urinalysis) will be performed. The ASI-Lite, HRBS, CGI-O, CGI-S, AISRS, and End of Trial form (if they complete the study before Week 12) will be completed in addition to the scheduled weekly assessments. Methamphetamine and creatinine and other drug urine tests, alcohol breathalyzer, if necessary, according to institutional policies, and SUR will be completed.

12.6 Drop-Out Prevention

Subjects will be encouraged to come for CBT sessions and for the clinical evaluations as described in this protocol. To minimize missed sessions, they will be reimbursed for transportation and time spent in completing study assessments. It will be emphasized to subjects during screening that even if they have a relapse they should come to all scheduled appointments. They will be discouraged from using methamphetamine, but there will be no penalty for relapsing or for missed sessions.

Subjects will be encouraged to complete study visits, assessments, and CBT sessions, even if they are unable to tolerate the investigational products. If a subject decides to drop out of the study prior to week 12, s/he will be asked to complete all final assessments (termination) at the time of drop out. If a subject wishes to stop taking the investigational product but to continue to participate in CBT sessions, s/he will continue to have all scheduled assessments according to the protocol and will complete the study at Week 16.

A subject will be considered a drop out, if the subject misses six consecutive visits during the 12 weeks of study interventions. However, s/he will be asked to complete all termination assessments at the time of drop out and will be compensated for completing these assessments.

Subjects are free to discontinue the study and to refuse to participate in any of the procedures. If a subject drops out without making their intentions known, staff will attempt to contact them by telephone or written correspondence. Once the subject has been contacted and expresses their decision to discontinue from further participation in the study, the research staff will cease to try to make further contact.

12.7 Follow-up (Weeks 13 - 16)

Subjects will be asked to return to the clinic once per week for 4-weeks after the completion of the study intervention phase of the trial. Subjects will receive CBT, and will be asked to provide a urine specimen for methamphetamine/creatinine and urine drug screen, to provide a self-report for use of methamphetamine, cocaine, opiates, alcohol, cigarette smoking, and marijuana, and will be asked about AEs and concomitant medication use. The subject will complete the follow-up form at Week 16. If it is not possible to arrange for the subject to return to the clinic, then they should be telephoned and asked to provide a current self-reported methamphetamine and other drug use and other current treatment for drug or alcohol abuse. Concomitant medications

and AEs will be assessed over the telephone as well as the follow-up form. If a subject cannot be contacted directly, attempts will be made to reach the individual(s) previously identified by the subject as a contact source.

12.8 Maintaining and Breaking Study Blind

The decision to break the study blind for an individual subject lies with the site principal investigator and project principal investigator or with the NIDA medical monitor, but should be resorted to only in cases of life-threatening emergency when knowledge of the investigational product identity will influence clinical management. KAI will develop an unblinding procedure for the study and ensure that emergency unblinding is possible 24 hours a day, seven days a week. This procedure could include leaving treatment information in a sealed envelope with a medical monitor, pharmacist or other designated individual at the participating center.

12.9 Safety Procedures

Subjects judged by the site principal investigator and/or study physician at any point to be a danger to self or others or who are judged to be in grave danger due to continued investigational product use and/or to extreme psychiatric problems will be discontinued from the study and connected with an appropriate treatment agency.

12.10 Subject Compensation

Subjects will be reimbursed for travel expenses, for providing data, and for time contributed to this research study in accordance with local site's IRB policies.

12.11 Subject Confidentiality

To maintain subject confidentiality, all laboratory specimens, eCRFs, reports, and other records will be identified by a coded number and name code only. Research and clinical records will be stored separately in a secure location and only the investigative staff will have access to the records. Subject information will not be released without the written permission, except as necessary for monitoring by the FDA, NIDA, its designees, or other regulatory agencies. Upon approval of the study by the site IRB, an application will be filed with NIDA for a certificate of confidentiality.

12.12 Study Termination

12.12.1 Subject Termination

An investigator may terminate a subject if s/he deems it clinically appropriate or for any of the following reasons: (1) significant side effects from investigational products, (2) serious or unexpected AEs, (3) failure to comply with the study protocol, (4) protocol violation, (5) positive pregnancy test, (6) serious intercurrent illness or a benzodiazepine or barbiturate medication use (see below), and (7) the subject becomes a danger to self or others. Persistent alcohol abuse will be assessed by the PI or study physician and after the third warning and consultation with NIDA, the subject may be terminated from the study.

Benzodiazepine and Barbiturate Abuse. If a subject is found to be persistently abusing a benzodiazepine or barbiturate medication while in the study, they will likewise be given a warning by the site principal investigator or study physician to stop using these drugs, and continued abuse of a benzodiazepine or barbiturate beyond 3 weeks after the date the warning was given may result in discontinuation of bupropion. A three-week interval is warranted due to the long elimination time of some benzodiazepines. If a subject is prescribed a benzodiazepine or barbiturate for legitimate medical purposes, subjects will be warned that any abrupt discontinuation of either medication is known to lower seizure threshold.

Failure to comply with protocol. A subject will no longer be eligible for study participation, if s/he is absent from the clinic for more than two consecutive weeks and does not provide any data. A subject's study participation will end if s/he fails to provide six consecutive urine samples. In any event, subjects will be contacted 4 weeks after completing study interventions to schedule a follow-up interview.

Voluntary withdrawal. A subject may withdraw from the study anytime s/he wishes. In the event a subject is discontinued from receiving the investigational products, s/he will be allowed to continue the CBT with the approval of the site principal investigator.

Any subject, who discontinues prematurely, regardless of the reason, will be requested to return for a final visit to perform the necessary procedures and obtain data for the final assessments to be completed at the end of the study intervention phase as well as 4 weeks later for the follow-up interview.

If at any time during the course of the study, psychiatric symptoms are so severe as to require medication outside of the protocol and/or hospitalization, the participant should be terminated from the study protocol and treated clinically. Study participants withdrawn from the protocol secondary to a medical or psychiatric concern will be referred for appropriate treatment. Subjects will be asked to sign a general consent for the release of information to the referred health care. Study staff may request transportation for emergency treatment of a subject if medically appropriate (e.g., for acutely psychotic or suicidal subjects).

All study participants will be advised to carry an emergency wallet card that identifies them as a participant in a clinical research study. The card will provide the name and phone number of the site principal investigator (physician) at the site who can be contacted in the event of an emergency. If possible, the card should also instruct the non-study physician rendering emergency care to provide information to the study physician with regards to that care.

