4.2.5 Safety of Bupropion

Contraindicated Conditions. Bupropion (ZYBAN Package Insert March 2007) is contraindicated in subjects:

- 1. With a seizure disorder.
- 2. Who are concurrently using a bupropion containing medication because the incidence of seizure is dose dependent.
- 3. Who have a current or prior diagnosis of bulimia or anorexia nervosa because of a higher incidence of seizures noted in patients treated for bulimia with the immediate-release formulation of bupropion.
- 4. Who are abruptly discontinuing alcohol or sedatives (including benzodiazepines).
- 5. Who are concurrently taking a monoamine oxidase (MAO) inhibitor (at least 14 days should elapse between discontinuation of an MAO inhibitor and initiation of bupropion administration).
- 6. Who have had an allergic response to bupropion.
- 7. Who have major depressive disorder (patients may experience worsening of their depression and/or the emergence of suicidal ideation and behavior (suicidality) or unusual changes in behavior, whether or not they are taking antidepressant medications, and this risk may persist until significant remission occurs). There has been a long-standing concern that antidepressants may have a role in inducing worsening of depression and the emergence of suicidality in certain patients.

AEs Associated With the Discontinuation of Treatment. AEs leading to discontinuation of treatment with bupropion SR included nervous system disturbances 655 (3.4%), primarily tremors, and skin disorders (2.4%), primarily rashes.

Incidence of Commonly Observed Adverse Events. The most commonly observed AEs (those that consistently occurred at a rate of 5 percentage points greater than that for placebo across clinical studies) consistently associated with the use of bupropion SR were dry mouth and insomnia.

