9.2 Exclusion Criteria

Participants must not:

1. Have current dependence, defined by DSM-IV criteria, on any psychoactive substance (e.g., opioids) other than methamphetamine, nicotine, alcohol or marijuana or have physiological

dependence on alcohol or a sedative-hypnotic (e.g., a benzodiazepine) requiring medical detoxification.

- 2. Have a current or past history of seizure disorder, including alcohol- or stimulant-related seizure, or significant family history of idiopathic seizure disorder.
- 3. Currently be using drugs that lower seizure threshold.
- 4. Have a history of head trauma that resulted in neurological sequelae (e.g., loss of consciousness greater than 5 minutes, or that required hospitalization).
- 5. Have psychiatric disorders, such as major current depression, psychosis, bipolar disorder, organic brain disorder, or dementia as assessed by the MINI interview, or medical disorder, any of which require an excluded medication (e.g., antidepressant, neuroleptic, systemic corticosteroid, xanthine) or which would make medication compliance difficult. Have had electroconvulsive therapy within the past 90 days before screening.
- Have a current suicidal ideation/plan as assessed by the MINI interview or HAM-D question #3. Current is identified as within the past 30 days.
- 7. Have a current or past history of anorexia nervosa or bulimia disorder.
- 8. Have serious medical illnesses or neurological disorders including, but not limited to, uncontrolled hypertension (See NIDA Guidelines on Hypertension in the Operations Manual, stage 1 hypertension allowed, but not stage 2 hypertension), significant heart disease (including myocardial infarction within one year of enrollment), angina, hepatic or renal disorders, renal insufficiency (plasma creatinine > 1.7 mg/dL), Parkinson's disease, active syphilis that has not been treated or refuse treatment for syphilis (see note), or have had therapy with any opiate-substitutes (methadone, LAAM, buprenorphine) within 2 months of enrollment, or any serious, potentially life-threatening or progressive medical illness other than addiction that may compromise subject safety or study conduct. Any ECG/cardiovascular abnormality (e.g., QTc interval prolongation > 450 milliseconds in men or 480 milliseconds in women), which in the judgment of the investigator is clinically significant.

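### Section 12.12.1 tells subjects abusing sedatives to stop, but requires the abrupt-discontinuation caution only for subjects with a legitimate prescription

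*Protocol*

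**What the plan says.** The contraindication list in Protocol 4.2.5 has as item 4 subjects "Who are abruptly discontinuing alcohol or sedatives (including benzodiazepines").

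The benzodiazepine and barbiturate paragraph of 12.12.1 has three sentences:

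- A persistent abuser of either drug class is to be "given a warning by the site principal investigator or study physician to stop using these drugs". Abuse that continues "beyond 3 weeks after the date the warning was given may result in discontinuation of bupropion".
- The interval is explained by pharmacokinetics: "A three-week interval is warranted due to the long elimination time of some benzodiazepines".
- The seizure-threshold caution applies where the subject is "prescribed a benzodiazepine or barbiturate for legitimate medical purposes, subjects will be warned that any abrupt discontinuation of either medication" lowers that threshold.

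Three other provisions bear on the point. Section 12.12.1 lets an investigator terminate a subject when clinically appropriate or for listed reasons, of which (6) is "serious intercurrent illness or a benzodiazepine or barbiturate medication use (see below"). Section 12.9 says that subjects "judged to be in grave danger due to continued investigational product use and/or to extreme psychiatric problems will be discontinued from the study". Exclusion criterion 1 in 9.2 begins "Have current dependence, defined by DSM-IV criteria, on any psychoactive substance (e.g., opioids) other than methamphetamine, nicotine, alcohol or marijuana" and goes on to bar physiological dependence on alcohol or a sedative-hypnotic that needs medical detoxification.

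For alcohol, 12.12.1 says that persistent abuse is assessed by the investigator or study physician, and that the subject may be terminated after a third warning and consultation with the sponsor.

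**The concern.** The protocol recognises the hazard twice: as a contraindication in 4.2.5, and in the caution itself in 12.12.1. Yet the caution is attached to subjects with a prescription, while the subjects told to stop are those abusing the drug. A site that follows the paragraph as written can tell a subject to stop without saying that the manner of stopping matters. If that subject stops abruptly, he or she is in a listed contraindicated state, and the paragraph says nothing about the product.

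What is at stake is seizure risk. The seizure text in 4.2.5 already counts excessive sedative use and stimulant addiction among the circumstances that raise it, and every randomized subject has methamphetamine dependence.

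**Working it through.** No arithmetic applies: the point depends on no rate, power figure or sample size. The check sets the relevant texts side by side.

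1. **Who is told to stop?** Persistent abusers of a benzodiazepine or barbiturate (12.12.1, first sentence of the paragraph).
2. **Who must receive the abrupt-stop caution?** Subjects with a legitimate prescription (third sentence). The protocol does not extend it to the group in step 1.
3. **What product action does the paragraph attach?** One, and it is permissive: possible discontinuation if abuse continues past 3 weeks. Of the three sentences, none says what to do about product when a warned subject complies by stopping abruptly.
4. **Is that state relevant to bupropion?** Yes, by 4.2.5 item 4.
5. **Does another section fill the gap?** Exclusion criterion 1 applies at entry, whereas the paragraph concerns abuse while on study. The prohibited-medication list in 12.13 names neither drug class. Section 11.1 asks for a three-day taper of investigational product before premature termination, but does not deal with sedative withdrawal. Reason (6) in 12.12.1 is permissive and refers the reader to the same paragraph. Section 12.9 is mandatory, but only once grave danger is judged. None requires the caution for warned subjects or names abrupt sedative withdrawal.
6. **Does the same hold for alcohol?** Item 4 covers alcohol too. Exclusion criterion 1 admits alcohol-dependent subjects unless they need medical detoxification, and 12.12.1 provides for warnings about persistent alcohol abuse without attaching the caution. A correction limited to sedatives would leave part of the mismatch in place.
7. **Is the wording suited to a blinded trial?** The paragraph speaks of discontinuing bupropion. Under 12.4 site staff do not know the assignment, so the rule can only operate on investigational product in either arm.

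**The case against.** The strongest reply is that the protocol contradicts nothing and that clinical judgment covers the case. Much of this stands.

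- A reader might infer that the protocol directs abrupt withdrawal. It does not. The instruction is to stop, it comes from the site principal investigator or study physician, and the stated consequence waits 3 weeks. The gap matters only if no advice is given on how to stop and the subject then stops at once.
- A reader might infer that product can be discontinued only after 3 weeks of continued abuse. The paragraph does not say only. Reason (6) allows termination for benzodiazepine or barbiturate use with no waiting period, and 12.9 compels discontinuation where grave danger is judged.
- A reader might infer that warned subjects go uncautioned in practice. That is unknown. The consent pages were removed from the text reviewed and the operations manual is not shown; either may carry the caution.
- A reader might infer that a mandatory, immediate stop of product is needed. Three things count against it. It would have to be reconciled with the three-day taper in 11.1. The trigger is hard to observe: on-study central testing (13.6.29) screens benzodiazepines in the first sample of the week and does not list barbiturates, and the Substance Use Report (13.6.31) asks about neither. The benefit is also partial, because mean terminal half-lives in 4.2.3 run from about 21 hours for bupropion to 37 hours for one active metabolite.
- Section 4.2.5 does advise stopping product after an allergic reaction, another listed contraindication. That concerns a reaction to the product itself, so it is weak evidence that an equivalent rule was omitted here.

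What survives is narrow: as written, the caution is required for one group and the instruction to stop goes to another.

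**Conclusion.** The point holds as a minor safety correction. Section 12.12.1 ties the abrupt-discontinuation caution to legitimately prescribed users and does not require it for the subjects it tells to stop, although 4.2.5 item 4 makes abrupt discontinuation of alcohol or sedatives a contraindication.

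The number of subjects affected cannot be derived from the protocol. It is probably small, because a subject who entered without sedative dependence would have to develop persistent abuse during the 12 weeks of dosing and then stop abruptly. For alcohol the entry bar is looser, and the protocol gives no figure.

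The conclusion rests on the protocol text alone and assumes nothing about the consent form or operations manual. It does not affect the primary analysis, error rates or sample size.

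**What to change.** Amend the substance-abuse text of 12.12.1 as follows:

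- **(a)** Every subject using a benzodiazepine or barbiturate, prescribed or not, and every subject warned about persistent alcohol abuse, receives the abrupt-discontinuation caution and is told to consult the study physician before stopping.
- **(b)** If an abrupt stop is reported, the study physician promptly assesses the subject and decides whether to hold or stop investigational product. The text should say how that decision relates to the three-day taper in 11.1. Scheduled assessments continue as in 12.6.
- **(c)** The reference to discontinuing bupropion is changed to discontinuing investigational product.

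The cost is a short amendment, with IRB approval before implementation (14.2) at the 5 or more sites (section 7). No new visits or laboratory tests are needed; (b) acts on what is reported, so it will not catch every abrupt stop. A few subjects may have product interrupted. Having been randomized and dosed, they remain in the ITT population (15.3).

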12.12.2 Trial Discontinuation

NIDA has the right to discontinue the investigation at any time.

12.13 Concomitant Medications

Any medications (including prescription, over-the-counter, herbal supplements and health store products) to be taken during the study must be approved by the site principal investigator. Medications that should not be taken at any time during the study include:

- All antidepressants
- Neuroleptics
- Systemic corticosteroids
- Xanthines (i.e., theophilline, theophilline sodium glycinate and aminophylline)
- Medications that interfere with methamphetamine detection in urine samples (e.g. ephedrine and pseudoephedrine)
- Bupropion containing medications (i.e., Wellbutrin[®], Zyban[®])
- The antiretrovirals nelfinavir, and efavirenz
- Tramadol (Ultram, Ultram Extended Release)

13 CLINICAL EVALUATIONS

Clinical evaluations will be administered according to the schedule in **Table 1**. Assessments were chosen to minimize the research burden, yet collect adequate data to address study hypotheses.

13.1 SCREENING ASSESSMENTS

Prior to randomization into the study, subjects will be screened to determine if they meet eligibility requirements. In addition, certain baseline assessments that are part of eligibility determinations will also provide physiological, psychological, and disease status information prior to investigational product administration. Screening and baseline assessments may be performed concurrently; however, baseline assessments will include only those acquired during a 14-day consecutive period prior to randomization. An End of Trial eCRF must be completed if a subject fails to meet eligibility requirements or discontinues screening before eligibility is established.

- 1. Informed consent
- 2. Locator form
- 3. Demographics
- 4. Timeline follow-back for methamphetamine use in the prior 30 days
- 5. Quantity frequency interview
- 6. Psychiatric evaluation and MINI evaluation for DSM-IV diagnosis of methamphetamine dependence and Axis-I disorders
- 7. Adult ADHD interview (ACDS)
- 8. Medical history and Family History Questionnaire
- 9. Prior medications for the 30 days prior to informed consent
- 10. Infectious disease serology/Syphilis test
- 11. Alcohol breathalyzer
- 12. Physical exam
- 13. Vital signs
- 14. Hematology and blood chemistries
- 15. Blood for DNA analysis (for all subjects who consent to genetics part of study)
- 16. Blood for RNA analysis (for all subjects who consent to genetics part of study)
- 17. Blood for plasma BDNF levels (for all subjects)

- 18. Blood for baseline plasma bupropion levels (for all subjects but will only be analyzed for subjects who are randomized onto the study
- 19. Medical Urinalysis
- 20. Pregnancy Test
- 21. ECG
- 22. AEs at each visit
- 23. Concomitant medication use at each visit
- 24. ASI-Lite
- 25. HAM-D (performed weekly during screening/baseline period)
- 26. Urine drug screen onsite test device (3 times per week)
- 27. Urine Methamphetamine/Creatinine for Central Lab (3 times per week) Note: Assay for methamphetamine and creatinine as well as the urine toxicology screen will be performed only for urine samples collected from the subjects who are randomized into the study.
- 28. SUR (3 times per week)
- 29. CBT Compliance (two 60-minute sessions weekly, to be checked at every visit and verified with the CBT attendance log)
- 30. Eligibility Checklist (initial evaluation)

		Tab	le 1.	Over	view	of S	tudy A	sses	smer	nts								
Assessment Study Week	Screening -4 to -1	Baseline	Intervention Phase Follow-up															
		-2 to -1	1	2	3	4	5	6	7	8	9	10	11	12/ Term	13	14	15	16
Screening																		
Informed consent	Х																	
Locator Form	Х																	
Demographics	Х																	
Timeline follow-back (30 days)	Х																	
Quantity Frequency Interview	Х																	
MINI	Х																	
ACDS	Х																	
Medical and family ^a history	Х																	
Prior medications	Х																	
Infectious disease panel/RPR	Х																	
Alcohol breathalyzer ^b	Х	3 X/week	3X	3X	3X	3X	3X	3X	3X	3X	3X	3X	3X	3X	Х	Х	Х	Х
Safety																		
Physical exam	Х													X ^l				
Vital signs	Х		Х	Х	Х	Х	Х	Х	Х	Х	Х	Х	Х	Xl				
Hematology	Х													X ^l				
Blood chemistries	Х													Xl				
Medical urinalysis	Х													Xl				
Pregnancy test ^c	Х		Х			Х				Х				X ^l				
ECG	Х													X ^l				
Adverse events ^d	3X/week	3X/week	3X	3X	3X	3X	3X	3X	3X	3X	3X	3X	3X	3X	Х	Х	Х	Х
Concomitant medications ^d	3X/week	3X/week	3X	3X	3X	3X	3X	3X	3X	3X	3X	3X	3X	3X	Х	Х	Х	Х
Eligibility Checklist ^e	Х	Х																
Efficacy																		
ASI-Lite ^f	Х	Х												X				
AISRS		Х				Х				Х				X				
HAM-D	weekly	weekly		Х		Х		Х		Х		Х		X ^l				
BSCS		weekly	Х	Х	Х	Х	Х	Х	Х	Х	Х	Х	Х	X ¹			1	
CGI-S		weekly	Х	X	X	X	X	Х	Х	Х	Х	Х	Х	X ¹			1	
CGI-O		weekly	Х	Х	Х	Х	Х	Х	Х	Х	Х	Х	Х	X ^l				
HRBS		X	l	l	İ	1		İ –	1	1		İ –	1	X ^l	1	1	l	1
SUR	3X/week	3X/week	3X	3X	3X	3X	3X	3X	3X	3X	3X	3X	3X	3X	Х	Х	Х	Х
Urine methamphetamine/	3X/week	3X/week	3X	3X	3X	3X	3X	3X	3X	3X	3X	3X	3X	3X	х	х	x	X
creatinine ^g																		

Table 1. Overview of Study Assessments																			
Assessment	Screening	Baseline	Intervention Phase													Follow-up			
Study Week	-4 to -1	-2 to -1	1	2	3	4	5	6	7	8	9	10	11	12/ Term	13	14	15	16	
Urine bupropion/hydroxybupropion ⁿ			3X	3X	3X	3X	3X	3X	3X	3X	3X	3X	3X	3X					
Blood for DNA (genetics consent)	Х																		
Blood for RNA ^h (genetics consent)	Х							Х						X ¹					
Bupropion Plasma Levels ⁱ	Х							Х						X ¹					
BDNF Plasma Levels	Х							Х						X ¹					
Urine drug screen – onsite test device	3X/week	3X/week																	
CBT compliance	X ^k	X ^k	3X	3X	3X	3X	3X	3X	3X	3X	3X	3X	3X	3X	X ^m	X ^m	X ^m	X ^m	
Investigational Product compliance ^j			Х	х	Х	Х	Х	X	х	Х	Х	Х	Х	x ¹					
End of Trial form	X – if screen fail																	Х	
Follow-up questionnaire																		Х	

^a The family history questionnaire will only be done on subjects who consent to the genetics testing even if they are considered a screen failure for the bupropion/methamphetamine study.

^b An alcohol breathalyzer test will be performed in accordance with institutional policy and state law.

^c The pregnancy test on Day 1 must be performed prior to randomization and administration of the first dose of investigational product.

^d These assessments are performed after the first screening visit

^e Eligibility is checked during screening and at baseline visits as data become available such that if a subject does not meet inclusion or exclusion criteria, the subject is no longer screened.

^f The ASI-Lite will be performed during screening; however, if the entire screening/baseline period takes longer than 14 days, the ASI must be repeated such that the it is collected during baseline.

^g Assay for methamphetamine and creatinine as well as the urine toxicology screen will be performed only for urine samples collected from the subjects who are randomized into the study.

^h Blood for RNA analysis should be collected at the same time of day at every collection time point to control for circadian rhythm effects on expression. One RNA tube will be collected during screening/baseline and at all other time points during the intervention phase of the study.

ⁱ During the intervention phase, blood for bupropion levels will be taken before the daily dose.

^j Investigational product compliance is reviewed at every clinic visit with the subject by self report but the pill count is only done weekly.

^k Two 60 minute early recovery skills group sessions given weekly until randomization occurs. Compliance should be checked at each visit and verified with the CBT attendance log.

¹ These assessments are performed at the last visit of Week 12 or at earlier termination.

^mCBT sessions are performed once a week during the follow-up period.

ⁿ Bupropion/hydroxybupropion will be analyzed after study closure only in those assigned to a bupropion treatment group as a surrogate marker for medication compliance.

